#### Research Design:

A total of 200 will be consented and 128 (64 per group, accounted for 36% dropout rate) patients will be randomized to be stratified based on their injury mechanisms (blast, non-blast) and headache severities (mild, moderate, severe) and enrolled over 6 years from VASDHS, and Naval Medical Center San Diego (MNCS). Patients meeting study enrollment criteria will be randomized into one of the two study groups (A&B) based on their mechanisms of injury, gender, severity of headache, and past failed therapies for their headache. The overall study duration for each subject is about 14 weeks developed into three phases according to the following schedule:

- 1) PRE-TREATMENT PHASE (weeks 1-2) consists of Visit 1 (Screening Visit) and Visit 2 (Pre-treatment Assessments);
- 2) TREATMENT PHASE (week 3-4) consists of Visits 3-12 (Neuronavigation guided rTMS consisting of 10 weekday treatments at  $>24$  and  $< 72$  hours apart, weekends excluded, maximum 5 weeks for treatment completion) rTMS will take place in Building 23 Room 105 at the VASDHS; and

3) POST-TREATMENT PHASE (week 5-14) consists of two initial weekly visits (Visits 13&14) and two additional biweekly visits (Visits 15&16) and one monthly visit (Visit 17).

Brain anatomical and functional MRI will be performed within 72 hours after Visits 2 and 13. Subjects will be required to fill out headache diary between assessment visits. Headache assessments along with quality of life, mood and functions assessments will be carried out at Visits 1,2, and 13--17. This frequency of treatment and duration of follow-up is in line with recently published rTMS articles related to TBI, headache and pain, and also in accordance with the 3-month post treatment initiation follow-up guideline /recommendation [32; 55; 80].

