For hypotheses 1 and 2, where multiple analyses are conducted, correction for family-wise Type I error rates will be made using the Westfall-Young randomization maxTprocedure, which adjusts p-values for significance while taking into account the correlation of the outcomes [76]. In this way, the study can control for an overall family-wise error rate of .05 while achieving more power than Bonferroni adjustments. Using this method of power analysis, the investigators estimated a sample size of 128 (64 per group, accounted for a 20% dropout rate) provides the study with 85% power

to detect a medium effect size (RMASS program provided by Hedeker) [25; 26]. Medium effect sizes were used based on the results included in the above sections. Medium effect size is defined as a between-group difference increasing linearly from 0 at baseline to .5 SD units at the last time point. The minimum power estimation is based on sample size calculation for 10% and 20% attrition, correlations of 0.2, 0.5, and 0.8 between the repeated measures, and for medium and large effect sizes. Data will be analyzed using SPSS version 23, all analyses will be two-tailed, where applicable with  $\alpha = .05$ .

**Hypothesis #1:** Active rTMS at LMC provides significantly more reduction in headache intensity, duration and frequency of exacerbation than sham rTMS.

Independent Variables: Treatment Groups with two levels (Groups A & B), Visits up to 8 (See below). Dependent Variables: Primary outcome: Average daily headache assessments (B1, B2, B3, B4, B5, B6); Secondary outcome: Debilitating Headache Composite Score (B1, B2, B3, B4, B5, B6); M-VAS Scores of headache (Visits 2, 7, 12, 13, 14, 15, 16, 17); HTL-6 and NSI (Visits 2,13,14,15, 16, 17); headache rescue medication usage (Visits 2,13, 14, 15,16, 17). Note, not all variables are collected at all visits.

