increased power to detect effects and precision for the estimation of the effect sizes without requiring increased sample size, and provide the study with a uniform method of data analysis for all hypotheses that include multiple measurements from the same subjects. The mixed effects model method provides an estimate of the individual variability around the population trend, the variability of the individual intercepts (baseline values) and slopes (changes across time), and the correlation between them. A fully saturated treatment by time model will be utilized for inference. Co-variance structure will be chosen based on Akaike's Information Criterion (AIC). This allows for any group level effects to be incorporated into the model. Denominator degrees of freedom will be calculated using the Kenward-Roger small sample correction. Analyses will be conducted within and across nested levels of the study design; this will involve within-subject analyses (comparison of occasions of measurement nested within an individual), as well as between-subject analyses (comparison of two groups). In addition, any treatment group comparison can be adjusted for subject-specific characteristics and adjustments for changes in these characteristics over the course of the study, and incorporated into the single-subject analyses. Based on investigators' experience with previously completed studies, we expect a dropout rate of 10 to 20% throughout the study. All analyses will be two-tailed, where applicable, with  $\alpha = .05$ . Correction for family-wise Type I error rates will be made using the Westfall-Young randomization maxT procedure, which adjusts p-values for significance while taking into account the correlation of the outcomes [70]. In this way we can control for an overall family-wise error rate of .05 while achieving more power than Bonferroni adjustments.

**Hypothesis #2:** Active rTMS at LMC provides significantly more improvement in quality of life, mood and functions than sham LMC stimulations.

Independent Variables: Treatment Groups with two levels (Groups A & B), Visits with 8 levels: pre-treatment (Visit 2), treatment (Visits 7 & 12), and Post-treatment (Visits 13, 14, 15, 16, 17).

Dependent Variables: Attention (CPT II), Memory (Hopkins Verbal Learning Test) Execute function (Trail Making Test A and B, and Stroop Test), Hamilton Depression Scale, SF-36 and BPI.

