Statistical Analysis: Data will be analyzed similar to hypothesis 1 and we estimated to have a minimum power of 85% for these analyses using similar method described above.

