### **Assessment Based Visits – Pre-treatment assessments (V2a), Post-TX 1-week (V13a), Post-TX 2-week (V14), Post-TX 4-week (V15), Post-TX 8-week (V16) and Post-TX 12 week (V17)**

Pre and post-treatment assessments will be conducted over video call, and questionnaires to be completed by subjects will be provided prior to each visit through MyHealtheVet or mailed to the subjects. Subjects will be given the choice to either: 1) complete questionnaires within 24hours of their video appointment and

return them through MyHealtheVet or FAX; or 2) complete them during the video call where subjects will provide their verbal responses and the study coordinator will document the response. The following assessment will have changes on administration:

1. Mechanical Visual Analogue Scale (MVAS) of Headaches, Muscle, and Joint Pain: subjects will rate their pain on the 0-100 MVAS scale at all On-site visits

The following assessments will not be conducted as they require in-person administration:

1. Stroop Test
2. Eye Tracking Assessment
3. Conner's Performance Test II
4. Trail Making Test

These assessments are part of the secondary hypothesis, measuring attention and executive functioning. Though these functions will not be measured, the primary aim of this study is to assess headache and quality of life and assessments related to the primary aim will still be administered.

All other assessments listed in the protocol will be administered with no changes, other than being conducted remotely. Subjects will continue to keep a daily log of their headaches and medication usage throughout the course of the study which will be collected by either sending it through MyHealtheVet or through FAX.

The following table summarizes the assessments/questionnaires administered:

Visit		2	2	3-	1	1	1	1	1
		a	b	12	3	3	4	5	6
					a	b			
Location		T	O	O	S	T	O	T	T
		H	S		H	S	H	H	H
Brief Pain Inventory-Short Form (BPI)	Self-administered		x		x		x	x	x
Neurobehavioral Symptoms Inventory (NSI)	Self-administered		x		x		x	x	x
		x		x	x		x	x	x

Headache Impact Test (HIT-6)	Self-administered					
Short Form Health Survey-36	Self-administered	x	x	x	x	
Hopkins Verbal Learning Test (HVLT)	Study Coordinator	x	x	x	x	
Hamilton Rating Scale for Depression (HRSD)	Study Coordinator	x	x	x	x	
Clinician-Administered PTSD Scale (CAPS-5)	Study Coordinator	x	x	x	x	
Modified Fatigue Impact Scale	Self-administered	x	x	x	x	
MVAS – Sliding Scale	Study Coordinator	x x	x	x	x	

TH: Telehealth; OS: On-site

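### Hypothesis 2 still claims a minimum power of 85% for attention and executive-function tests that the telehealth schedule no longer administers

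*Combined protocol and SAP*

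**What the plan says.** Section 9, Hypothesis #2, names the outcomes: "Dependent Variables: Attention (CPT II), Memory (Hopkins Verbal Learning Test) Execute function (Trail Making Test A and B, and Stroop Test", followed by the Hamilton scale, SF-36 and BPI. The analysis paragraph below it gives one power figure for the whole set: "we estimated to have a minimum power of 85% for these analyses using similar method described above".

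The method referred to is in Data Management, Analysis and Power Calculations: "a sample size of 128 (64 per group, accounted for a 20% dropout rate) provides the study with 85% power". The effect is defined there as a "between-group difference increasing linearly from 0 at baseline to .5 SD units at the last time point". Correlations of 0.2, 0.5 and 0.8 between repeated measures are listed. A Westfall-Young maxT correction applies to hypotheses 1 and 2, so that "the study can control for an overall family-wise error rate of .05".

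The COVID-19 design changes, made to reopen enrolment, move baseline and follow-up assessments to telehealth. Under Assessment Based Visits, Stroop, eye tracking, CPT II and Trail Making are listed as not conducted. The protocol attributes them to the secondary hypothesis and adds: "Though these functions will not be measured, the primary aim of this study is to assess headache and quality of life".

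**The concern.** Three test batteries remain confirmatory outcomes in the analysis text, while the schedule for newly enrolled patients does not collect them. Because Visit 2a is itself a telehealth visit, a patient enrolled under that schedule has no value on these tests at any visit. The mixed model tolerates missing visits, but a patient with no observation on an outcome adds nothing to that outcome's analysis. The effective sample is the patients tested in person, some perhaps with only part of their follow-up.

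Two things are at stake. A null result on attention or executive function would be read against 85% power that nobody has shown to apply. And if the choice to keep or drop these outcomes from the maxT family is left until the data are seen, it becomes a post hoc change to the family.

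**Working it through.** **Inputs from the plan.** 64 per arm, 1:1; 20% dropout; two-sided alpha 0.05; difference rising linearly from 0 to 0.5 SD; correlations r = 0.2, 0.5, 0.8. Hypothesis #2 gives eight visit levels (Visits 2, 7, 12, 13-17). Research Design supports six for the function tests (Visits 2, 13-17). The 36% dropout in Research Design matches the step from 200 consented to 128 (128/200 = 0.64), so 20% is used for loss after randomisation.

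**Assumptions.** Equally spaced visits, compound symmetry, a single outcome with no maxT adjustment, and the same remote share in each arm. Remote patients contribute no data on these tests.

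**Step 1: reproduce the 85%.** With time scaled 0 to 1 and complete data, the arm difference in slope has

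SE = sqrt[ 2(1 − r) / (n × S) ], with S the sum of squared deviations of time, and power = Φ(0.5/SE − 1.96).

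Six visits give S = 0.70. Taking dropout up front, n = 64 × 0.8 = 51.2. At r = 0.5, SE = sqrt[1/(51.2 × 0.70)] = 0.167 and power = Φ(2.993 − 1.96) = 0.849. This matches the stated 85%. First-order autoregressive variants with 51.2 per arm give 0.44 to 0.56 and do not.

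**Step 2: gradual attrition.** Retention falls linearly to 80% by the last visit. With six visits, 4% of patients are last seen at each of visits one to five and 80% at the sixth. With eight, 0.2/7 are last seen at each of the first seven. The information matrix per patient is M = Σ p_k X_k′ R_k⁻¹ X_k, where X_k holds intercept and time for the first k visits. The slope information is I = 1/[M⁻¹] at the slope element, and SE = sqrt[2/(n × I)].

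- Six visits: I = 0.765 (r = 0.2), 1.199 (r = 0.5), 2.960 (r = 0.8).
- Eight visits, r = 0.5: I = 1.468.

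Example, six visits and r = 0.5. With everyone tested, SE = sqrt[2/(64 × 1.199)] = 0.161 and power = Φ(3.097 − 1.96) = 87%. With 25% remote, n = 48, SE = 0.186 and power = Φ(2.683 − 1.96) = 77%.

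**Step 3: power for CPT II, Trail Making and Stroop, with n = 64 × (1 − remote share).**

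| Setting | 0% remote | 25% | 50% | 75% |
|---|---|---|---|---|
| Six visits, r = 0.5 | 87% | 77% | 59% | 34% |
| Six visits, r = 0.8 | 99.8% | 99% | 93% | 68% |
| Eight visits, r = 0.5 | 93% | 84% | 68% | 40% |
| Six visits, r = 0.2 | 70% | 57% | 42% | 24% |

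**Step 4: break-even.** Patients per arm needed for 85%: n = 2 × (1.96 + 1.036)² / (0.25 × I). This gives 60 per arm (six visits, r = 0.5), 49 (eight visits, r = 0.5) and 25 (six visits, r = 0.8). The remote shares that still leave 85% are therefore about 6%, 23% and 61%. With dropout taken up front as in Step 1, the r = 0.5, six-visit case needs all 64, so there is no slack.

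**The case against.** The strongest reply is that nothing in the documents shows how many patients were tested in person. Enrolment had begun before the change, and some patients were already in follow-up. A reader might infer that the amended design cannot deliver 85% for these tests. The documents do not support that: r = 0.8 is one of the plan's own values, and with six visits it leaves 93% power when half the patients are remote. With eight visits and r = 0.5, a 25% remote share gives 84%, practically the stated figure. This objection stands and limits the claim to the loss of a guaranteed minimum.

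A reader might also infer that these outcomes are now nearly empty and impose a new multiplicity penalty on the others. The first part is unknown. The second does not follow. These outcomes were always in the family, so the amendment adds no penalty, and maxT allows for correlation between outcomes. Keeping them can only raise the critical value relative to a family without them, but by how much cannot be computed from the documents.

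The 70% at r = 0.2 with everyone tested is not caused by the telehealth change. It is a separate fault in calling 85% a minimum over the listed correlations.

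Finally, the protocol openly discloses that these functions will not be measured, and it keeps the other hypothesis 2 measures. That is true, but disclosure in the COVID-19 section does not amend the analysis text.

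**Conclusion.** The inconsistency is real and is in the current text. For CPT II, Trail Making and Stroop, 85% is no longer a minimum, because it was computed on 128 patients and every patient on the telehealth schedule is lost to these tests. At 25% to 75% remote, power lies between 77% and 34% at r = 0.5 with six visits, and between 99% and 68% at r = 0.8. Where the trial falls depends on the number tested in person and the correlation, and the documents give neither for these tests. The figures rest on compound symmetry, 20% attrition and an unadjusted alpha of 0.05. They treat each remote patient as wholly untested, although someone who changed schedule mid-study may have partial data. The removal does not affect the power statement for Hopkins, Hamilton, SF-36 and BPI. No sum in the plan is wrong on this point. The analysis text was left unrevised after the design changed.

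**What to change.** Before unblinding, reconcile the Hypothesis #2 outcome list and power sentence with the telehealth assessment list:

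1. Limit the 85% statement to outcomes collected under both schedules (Hopkins, Hamilton, SF-36, BPI), and state the correlation and number of visits behind it.
2. Define the hypothesis 2 maxT family as those same outcomes.
3. Report how many patients in each arm have each dropped test, at baseline and at follow-up.
4. Report CPT II, Trail Making and Stroop as exploratory between-arm estimates with confidence intervals in patients tested in person, with power or precision restated from that number.

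Purely descriptive reporting is not required. Patients tested in person are still a randomised 1:1 comparison, only a smaller one. The change is wording only. Its cost is giving up the confirmatory claim on attention and executive function.

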**Exploratory aims:**

- 1) Explore the treatment effect on resting state supraspinal functional connectivity;
- 2) Explore moderators' effect of injury mechanisms (blast and non-blast) and the headache severity on the treatment outcomes.

Effect of treatment on the resting state supraspinal functional connectivity will be explored by using Self-organizing Group Level Independent Component Analysis (SogICA)[15; 28]. Primary focus will be placed on the medioprefrontal cortices (MPFCs) and the anterior cingulate cortex (ACC) regions, which were found to have altered functional connectivity in the MTBI patients in comparison to healthy controls in a recently published study conducted by the investigators [44]. These regions will serve as the primary seeded regions for subsequent pre- and post-treatment between-group ANCOVA resting state functional connectivity analyses. Additional levels of exploratory analyses will also include baseline between-group assessments with and without factoring in the mechanisms of injury and headache severities. For exploratory aim #2, the Injury mechanism (blast vs. non-blast) will be explored by adding it as independent variables to the mixed model. The effect of initial headache severity (Visit 2) will be explored by adding this baseline outcome to the mixed model as a fixed covariate.

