## Section 6 - Specific Aims

### 6) Provide a statement of specific aims and hypotheses that serve as the basis for this protocol. Emphasize those aspects that justify the use of human subjects.

1) Compare the long term treatment effect of active rTMS (Group A) to sham LMC rTMS (Group B) in reducing the intensity, frequency and duration of MTBI-HA and the overall analgesic usage;

Hypothesis #1: Active rTMS at LMC provides significantly more reduction in headache intensity, duration and frequency of exacerbation than sham rTMS;

2) Compare the long term treatment effects of Group A to Groups B in improving quality of life, mood and functions in patients with MTBI-HA;

Hypothesis #2: Active rTMS at LMC provides significantly more improvement in quality of life, mood and functions than sham LMC stimulations;

Coinciding with the specific aims, the proposal also consists of the following exploratory aims:

1) Explore the treatment effect on resting state supraspinal functional connectivity in the pain related network;

2) Explore moderators' effect of injury mechanisms (blast and non-blast) and the headache severity on the treatment .

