## 4) Supraspinal Functional deficit in patients with MTI-HA

[figure not shown]
Our published studies with functional magnetic resonance imaging (fMRI) suggest that patients with persistent MTBI-HA have significant

compromised medial prefrontal modulatory response to heat pain stimuli and their resting state medial prefrontal cortical connectivities to other pain related regions are diminished in comparison to age and gender matched healthy controls (**See excerpted study figures 3&4 from appendix #6b**) [44].

]. Although a previous study suggested blast-related traumatic brain injury (TBI) appeared to have a unique effect on brain function associated with cognitive inhibitory tasks that could be distinguished from TBI resulting from non-blast (blunt or motor vehicle injury) related TBI [17], our preliminary assessment with experimental heat pain stimulation found no significant difference in supraspinal modulatory response to experiment heat pain between blast (n=7) and non-blast Veterans (N=7) ([name] et al., unpublished data). When turning our attention to assess the headache severity related supraspinal pain modulatory functions, we found Veterans with **Mild** ( $\leq 1$  4 on a 0-10 NRS, numerical pain rating scale) intensity of headache appeared to have higher level of left medial prefrontal cortical function in comparison to their counterparts with **Moderate-to-Severe ( $\geq 5$  on 0-10 NRS)** head ache intensity in their response to heat pain stimulation under functional magnetic resonance imaging (fMRI). Therefore further mechanistic exploration is required to understand the potential impact of injury mechanisms and headache severities on the treatment outcome.

**Figure 3.** Resting state functional connectivity difference with the left medial prefrontal cortex (seeded region) of the Healthy Controls ( $N = 15$ ) demonstrating more significant ( $P < 0.01$ ) functional connectivity to the left secondary somatosensory cortex (SSC2) and right inferior parietal lobe (IPL) than patients with mild traumatic brain injury ( $N = 15$ ).

**Figure 4.** Resting state functional connectivity difference with the right anterior cingulate cortex (seeded region) of the healthy controls ( $N = 15$ ) demonstrating less significant ( $P < 0.01$ ) functional connectivities to the right secondary somatosensory cortex (SSC2) and inferior parietal lobe (IPL) than patients with mild traumatic brain injury ( $N = 15$ ).

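### Exploratory aim 2 asks whether headache severity moderates the treatment effect, but the planned model enters severity only as a covariate and so cannot answer; for injury mechanism the plan needs one clarifying sentence.

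*Combined protocol and SAP*

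**What the plan says.** Section 6 (Specific Aims) sets the second exploratory aim: "Explore moderators' effect of injury mechanisms (blast and non-blast) and the headache severity on the treatment". The Exploratory aims part of Section 9 repeats it with treatment outcomes as the object. Section 7, Preliminary Data item 4, gives the motive: "further mechanistic exploration is required to understand the potential impact of injury mechanisms and headache severities on the treatment outcome".

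The Exploratory aims part of Section 9 gives the model terms, one sentence per moderator:

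- Mechanism: "the Injury mechanism (blast vs. non-blast) will be explored by adding it as independent variables to the mixed model".
- Severity: "The effect of initial headache severity (Visit 2) will be explored by adding this baseline outcome to the mixed model as a fixed covariate".

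The host model is described under Statistical Analysis for Hypothesis #1 as saturated for treatment by time. That is the only interaction stated. The same part says in general terms that group-level effects can be incorporated and that treatment comparisons can be adjusted for subject characteristics. Elsewhere, the two variables appear in balancing the allocation (Research Design; Process of randomization) and in baseline between-group comparisons in the imaging analysis.

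**The concern.** A moderator is a variable across whose values the treatment effect differs. Showing moderation requires a term that lets the treatment effect vary with that variable. A covariate without such a term shifts the expected outcome equally in both arms, so the model has one treatment effect per visit, the same at every severity. Its coefficient says whether subjects with worse headache at entry do worse later. It does not say whether rTMS works differently in them.

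Two misreadings could follow. A strong severity coefficient could be reported as moderation when it is only prognosis. A weak one could be reported as no moderation when the treatment effect does vary with severity.

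**Working it through.** **1. Aim against model term.**

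| Moderator | Aim | Term stated | Product with treatment stated? |
|---|---|---|---|
| Headache severity | moderation | fixed covariate | no |
| Injury mechanism | moderation | independent variable(s) | no, but possibly implied |

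The two labels differ. For Hypothesis #1 the plan writes "Independent Variables: Treatment Groups with two levels (Groups A & B), Visits up to 8", and those two factors are crossed in the saturated model. Calling mechanism an independent variable may therefore mean that it is crossed too. Severity is called a covariate, and no such reading is available for it. The word fixed could mean not random, or not varying over time; neither supplies a product term.

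**2. What a covariate-only term shows.** Simulation, n = 128, 4,000 runs, coefficients assumed:

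| Truth | Severity covariate significant | Treatment x severity significant |
|---|---|---|
| Prognostic only (0.5 SD per SD) | over 99.9% | 5.4% |
| Moderating only (effect differs by 0.5 SD per SD) | 6.3% | 78% |

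The covariate term detects prognosis and stays near the 5% level when severity only moderates.

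**3. The plan's own power figure.** The documents give none for this aim. For the two-group comparison they state "64 per group, accounted for a 20% dropout rate) provides the study with 85% power", with a "between-group difference increasing linearly from 0 at baseline to .5 SD units at the last time point". With 6 periods the slope difference is 0.5/5 = 0.1 per period, and the squared time deviations sum to 17.5. At correlation 0.5 (compound symmetry) with 64 x 0.8 = 51.2 per arm:

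- SE = sqrt(2 x 0.5/17.5/51.2) = 0.0334
- 0.1/0.0334 = 2.99, and 2.99 - 1.96 = 1.03, giving 84.9% power.

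The stated 85% is reproduced.

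**4. Scaling to an interaction.** For a binary moderator with share p, the interaction variance is the main-effect variance divided by p(1-p). Take the stated 85% as given (1.960 + 1.036 = 2.996) and suppose an interaction as large as the main effect:

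- 50:50 split: 2.996 x 0.5 - 1.960 = -0.462, power 32%.
- 30:70 split: 2.996 x sqrt(0.21) - 1.960 = -0.587, power 28%.
- 20:80 split: 2.996 x 0.4 - 1.960 = -0.762, power 22%.

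The blast share is an assumption; the documents do not give it.

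**5. Detectable interaction at the last period.** Assumed: 6 periods with the first as baseline, unit SD, 64 per arm, 20% dropout spread evenly over periods 2 to 6, outcome conditional on baseline, and generalised least squares with free visit means. The correlations 0.2/0.5/0.8 are those listed in the power section. AR(1) is added here because the plan leaves the covariance structure to AIC.

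| Severity interaction, SD per SD | Compound symmetry | AR(1) |
|---|---|---|
| 80% power | 0.54/0.47/0.32 | 0.55/0.55/0.51 |
| 85% power | 0.58/0.51/0.35 | 0.59/0.59/0.55 |

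A 50:50 binary moderator has SD 0.5, so its full-difference interaction is twice the per-SD figure: 0.65 to 1.11 SD for mechanism at 80% power and 0.69 to 1.18 SD at 85% (doubled before rounding).

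Hand check on a single endpoint with baseline correlation 0.5, using (1.960 + z) x sqrt(1 - 0.25) x 2/sqrt(N):

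- 80% power: 2.802 x 0.866 x 2/sqrt(128) = 0.43, and 0.48 at N = 102.
- 85% power: 0.46 and 0.51.

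These agree with the table.

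**The case against.** The strongest defence is that the plan names its purpose as moderation, the aim is exploratory, and nothing prevents the statistician from fitting an interaction to the planned data. That limits the importance of the point, and no power claim is at risk. It does not supply the missing term: the general remarks about group-level effects and adjustment describe covariate adjustment, and the severity sentence specifies something else.

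A reader might infer four stronger things, which the documents do not support:

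- *That the mechanism analysis is also wrong.* The wording may mean a cross with treatment, so this half is only a request to confirm.
- *That the main results are compromised.* Hypotheses 1 and 2 and their error control do not use these terms.
- *That the detectable mechanism interaction, 0.7 to 1.6 SD, dwarfs the planned 0.5 SD effect.* That range can be reproduced, but it comes from a last-minus-first contrast without adjustment for baseline, whereas the 0.5 SD is defined as a linear trend. On the same contrast the main effect detectable at 85% power is already 0.72/0.57/0.36 SD (compound symmetry) or 0.79/0.78/0.65 SD (AR(1)). The comparison is not like for like.
- *That keeping the baseline row dilutes the interaction.* It does so only if the moderator term is not crossed with visit: a true 0.30 becomes 0.30 x 5/6 = 0.25 with 6 periods, or 0.30 x 7/8 = 0.26 with 8 visits. It is a caution for one way of fitting the model, not a fault in the plan.

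**Conclusion.** The point holds for severity. As written, the analysis estimates prognosis and cannot show whether the treatment effect varies with initial headache severity. This follows from the model terms and depends on no sample-size figure. For injury mechanism the plan is incomplete in wording only.

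The consequence is confined to one exploratory aim, but half of that aim goes unanswered. The corrected analysis would be imprecise: about 0.65 to 1.2 SD for mechanism and 0.3 to 0.6 SD per SD of severity at 80 to 85% power. These ranges rest on the assumptions in step 5 of the working, above all the 50:50 blast split and the covariance structure. They describe what the corrected analysis could detect and are not evidence for the mismatch itself.

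**What to change.** In the Exploratory aims part of Section 9, replace the two sentences on aim 2 with text such as:

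*For exploratory aim 2, separate mixed models will include treatment x Visit 2 headache severity and treatment x injury mechanism, each crossed with visit or fitted to post-baseline visits only, with all lower-order terms. The interactions, and the treatment effects in blast and non-blast subjects and at stated severity values, will be reported with 95% CIs and labelled exploratory. A non-significant interaction will not be interpreted as absence of moderation.*

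Also name the severity score. A Visit 2 value exists for "M-VAS Scores of headache (Visits 2, 7, 12, 13, 14, 15, 16, 17"), but the primary diary outcome is averaged over between-visit periods, and the mild/moderate/severe categories in Research Design have no cut-points there. Preliminary Data item 4 uses a 0-10 scale with moderate-to-severe at 5 or more, but does not separate moderate from severe. Where the score is the outcome's own baseline value, use it as the covariate and leave that baseline row out of the response, keeping all later visits.

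Cost: a short text change and no data beyond those already scheduled. Crossing a moderator with treatment and visit adds 12 parameters with 6 periods (1 + 1 + 5 + 5) or 16 with 8 visits (1 + 1 + 7 + 7). A two-way term on post-baseline visits is leaner and also addresses the aim. The main downside is the low precision, which the plan should state.
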